11.1 ADVERSE EVENTS

AEs will be coded by system organ class and preferred term using the *Medical Dictionary for Regulatory Activities* (MedDRA), Version 21.1 or newer.

An AE will be considered a treatment-emergent adverse event (TEAE) if the AE began or worsened (increased in severity or became serious) on or after the date of the first dose of OL IP. Per eCRF instructions, a new AE record will be created with a new AE onset date for any AE that worsens. Therefore, TEAEs can simply be identified as those AEs with recorded onset date (and time, if known) on or after the date of the first dose of IP.

The number and percentage of patients reporting TEAEs during the OLTP will be tabulated by system organ class and preferred term; by system organ class, preferred term, and severity; and by system organ class, preferred term, and relationship to IP.

The number and percentage of patients reporting TEAEs during the DBTP will be tabulated for each treatment group by system organ class and preferred term; by system organ class, preferred term, and severity; and by system organ class, preferred term, and relationship to IP. The total number and percentage of TEAEs during the DBTP will also be summarized by severity and relationship to IP for each treatment group.

The number and percentage of patients reporting TEAEs during the OL SFU period will be tabulated by system organ class and preferred term for the OL Safety Population. The number and percentage of patients reporting TEAEs during the DB SFU period will be tabulated by system organ class, preferred term, and DB treatment group for the DB Safety Population.

For OLTP, DBTP, or SFU period, if more than 1 AE was coded to the same preferred term for the same patient, the patient will be counted only once for that preferred term using the most severe and most related occurrence for the summarization by severity and by relationship to IP.

An AE that occurs more than 30 days after the date of the last dose of DB IP or occurs after the last SFU visit (whichever comes last) will not be summarized except for AEs related to reported pregnancies. AEs associated with pregnancies reported in the protocol-required timeframe up to approximately 12 weeks following the last dose of DB IP will be summarized.

The number and percentage of patients with common ($\geq 2\%$ of patients in any treatment group) TEAEs will be summarized by preferred term for OLTP and be summarized by preferred term and treatment group for DBTP.

The number and percentage of TEAEs leading to premature discontinuation of IP during the OLTP will be summarized by preferred term. The incidence of AEs leading to premature discontinuation of IP during the DBTP will be summarized by preferred term and treatment group.

An AE will be considered a TESAE if it is a TEAE that additionally meets any SAE criterion.

Summary tables will be provided for patients with TESAEs if these occurred in 5 or more patients. The number and percentage of patients with TESAEs will be summarized for OLTP, DBTP, and SFU period.

For the Screened Population, listings will be presented for patients with SAEs, patients with AEs leading to premature discontinuation, and patients who die (if any). All patients with SAEs, including SAEs reported during the screening period and the SFU period, and patients discontinuing because of AEs occurring before the start of OLTP will be included in these listings.

The number and percentage of patients with any EPS TEAEs, EPS SAEs, and EPS AEs leading to premature discontinuation of IP will be summarized overall for the OLTP in the OL safety population and by treatment for the DBTP in the DB safety population separately.

The number and percentage of patients reporting TEAEs of ocular events of special interest will be summarized overall for the OLTP in the OL safety population and OL SFU period in the OL SFU population, by treatment for the DBTP and DB SFU in the DB safety population. A listing of all reported ocular events of special interest will be provided.

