8.9 Withdrawal Criteria

It is the right and the duty of the investigator or subinvestigator to stop treatment in any case in which emerging effects are of unacceptable risk to the individual patient. In addition, the investigator or subinvestigator is to stop treatment of any patient with unmanageable factors that may interfere significantly with the trial procedures and/or the interpretation of results.

A patient must be discontinued for any of the following reasons:

1. The patient is unable to tolerate the 4.5 mg/d dose.
2. The patient fails to attain *response threshold* by Week 8 (Visit 8) or stability of response threshold criteria by Week 10 (Visit 9) (see [Section 4.5](#));
3. After stability has been attained, except for the single allowed excursion above the response threshold prior to Visit 13/End of OL, there is a lack of ongoing stability as evidenced by PANSS total score increases by $\geq 30\%$ relative to Visit 2/Baseline; or PANSS item score is > 4 on one or more of PANSS items P1: delusions; P2: conceptual disorganization; P3: hallucinatory behavior; P6: suspiciousness/persecution; P7: hostility; G8: uncooperativeness; G14: poor impulse control; or CGI-S score increases by 2 or more points relative to Baseline/Visit 2;
4. The patient required or initiated hospitalization for his/her psychiatric symptoms (excluding the discretionary hospitalization stay, which is to end no later than Visit 3 [Day 8] of the OL treatment period, or extension of the initial hospitalization described in this protocol);
5. The patient took or required prohibited medication, including initiation of treatment with a mood stabilizer, antidepressant, antipsychotic agent, or with a benzodiazepine that exceeds the protocol-specified allowance or duration (ie, more than 2 mg/d of lorazepam or equivalent or for more than 3 consecutive days) to treat worsening symptoms of schizophrenia or any other psychiatric disorder as judged by the clinical impression of the investigator;

6. At the end of the OL treatment period, the patient does not meet all criteria to enter the DB treatment period ([Section 4.6](#));
7. Positive UDS after enrollment, confirmed by retest at next scheduled visit; for exceptions see [Exclusion Criterion 3](#) and [Section 4.8.3](#);
8. The patient meets the criteria for relapse during the DB treatment period;

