Open-label Treatment Period: Patients who continue to meet eligibility criteria at Visit 2/Baseline will enter an OLTP for up to 18 weeks. Patients need to respond to initial treatment (attain response threshold) and subsequently meet stability (confirmation of response threshold criteria at the subsequent visit) and then maintain it for an additional 8 weeks before being randomized.

Patients will receive OL cariprazine dosed as 1.5 mg/d beginning at Visit 2; titrated to 3.0 mg/d at Visit 3 (Day 8) and then titrated to 4.5 mg/d at Visit 4 (Week 2). Patients will continue on the 4.5 mg/d dose for the remainder of the OLTP. Following the dose increase to 4.5 mg/d, if there are significant tolerability issues, the investigator should utilize rescue medications as clinically appropriate. If further tolerability issues arise, a temporary drug holiday up to 3 days, patients who are unable to tolerate the 4.5 mg/d must be discontinued. Beginning at Visit 6 (Week 4), patients will be assessed for attainment of response threshold.

Double-blind Treatment Period: OL patients who are able to maintain the response threshold criteria for 8 weeks with no more than 1 excursion of response threshold criteria will be randomized 1:1:1 to receive cariprazine at the same dose (4.5 mg/d), a reduced dose (3.0 mg/d), or placebo for up to 26 weeks. Patients will continue to receive study treatment until a relapse event occurs or until completion of the 26 weeks of randomized treatment.

Safety Follow-up Period: Patients who complete the study, or who prematurely discontinue from either the OLTP or DBTP will be followed for 4 more weeks and will have 2 evaluations for safety assessments at Visits 27 (Week 46) and 28 (Week 48) during the SFU period. During the SFU period, patients will continue as outpatients and will receive treatment as usual at the discretion of the investigator or designee. Patients will not receive investigational product (IP) during the SFU period.

Treatment regimen and dosing is provided in protocol Section 5.5. The schedule of evaluations is presented in [Table 4-1](#) and [Table 4-2](#).

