9.0 EXTENT OF EXPOSURE AND TREATMENT COMPLIANCE

9.1 EXTENT OF EXPOSURE

Exposure to the OL IP for the OLTP will be summarized for treatment duration, calculated as the number of days from the date of the first dose of OL cariprazine taken to the date of the last dose taken during the OLTP, inclusive. Descriptive statistics (n, mean, SD, median, Q1, Q3, minimum, and maximum) will be presented.

Exposure to the DB IP for the DB Safety Population during the DBTP will be summarized for treatment duration, calculated as the number of days from the date of the first dose of DB IP to the date of the last dose of DB IP, inclusive. Descriptive statistics (n, mean, SD, median, Q1, Q3, minimum, and maximum) will be presented by treatment group.

Exposure to cariprazine during the entire study (OLTP and DBTP) will be summarized by intervals for the OL Safety Population. Descriptive statistics (n, mean, SD, median, Q1, Q3, minimum and maximum) will be presented.

By design, patients will take a fixed dose of cariprazine and there is no titration period during the DBTP. Mean daily dose, final dose will not be provided during the DBTP.

Patient-years, defined as exposure to the IP in years, will be summarized for the OLTP for the OL Safety Population. Patient-years will also be summarized by treatment group for the DBTP for the DB Safety Population. Patient years of exposure to cariprazine during the entire study (OLTP and DBTP) will also be summarized for the OL Safety Population.

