11.0 SAFETY ANALYSES

The safety analyses will be performed for the OL safety, OL SFU and DB safety populations. The summarization will be overall for the OLTP in the OL safety population and OL SFU period in the OL SFU population, and by treatment group for the DB period and the DB SFU period in the DB safety population. The summarization for the OLTP will use the OL safety population as the denominator. The summarization for the DBTP will use the DB safety population as the denominator. The summarization for the OL SFU period or DB SFU period will use the OL SFU population or the DB safety population as the denominator respectively.

Safety parameters will include adverse events (AEs), clinical laboratory parameters, vital signs, Electrocardiographic (ECG) parameters, ophthalmological parameters, Columbia–Suicide Severity Rating Scale (C-SSRS), and EPS scales, including Abnormal Involuntary Movement Scale (AIMS), Barnes Akathisia Rating Scale (BARS), and Simpson-Angus Scale (SAS).

For each safety parameter, the last assessment made before the first dose of OL IP will be used as the baseline for all analyses of that safety parameter, unless stated otherwise. Continuous variables will be summarized by number of patients and mean, SD, median, minimum, and maximum values. Categorical variables will be summarized by number and percentage of patients.

The derived visits in the DBTP will use the same strategy as described in Section 10.0. The detailed week mapping windows is provided in Section 16.1.

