14.0 DETERMINATION OF SAMPLE SIZE

The sample size and power calculations are based on the analysis of time to relapse in the DBTP to compare each cariprazine dose group versus placebo using a log-rank test. The trial will be a fixed follow-up design. Patients are followed from randomization until dropout, relapse or a fixed duration of 26 weeks.

Based on the results from RGH-MD-06, the relapse hazard ratio is assumed to be 0.50, and cumulative relapse rate at Week 26 for the placebo group is 46% (Study RGH-MD-06, 2015). In addition, the cumulative dropout rate due to reasons other than relapse at 26 weeks is assumed to be 20%.

Using these assumptions, a total of approximately 103 relapse events in the DB period need to be observed in order to have 85% power to detect a statistically significant difference between each cariprazine and placebo group, using 2-tailed, log-rank tests at an overall 5% level of significance. The trial should randomize approximately 345 patients, 115 patients each arm, to provide the required number of relapse events. EAST 6.0 was used for sample size and power calculation.

A fixed-sequence procedure will be used for multiple comparisons to control the family-wise Type I error rate at a 0.05 level. First, the cariprazine 4.5 mg/d group will be compared with the placebo group in the primary endpoint; if the test for cariprazine 4.5 mg/d versus placebo is significant at the 0.05 level, then cariprazine 3.0 mg/d arm will be tested versus placebo at 0.05 level.

Assume the screening failure rate is 34%, and approximately 33.3% of patients enrolled into the OLTP will be randomized into the DBTP. Then, approximately 1035 patients will be expected to be enrolled into the OLTP, and approximately 1569 patients are expected to be screened.

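### Double-blind adverse events are summarised by arm only as crude percentages although relapse ends treatment, so under the planned 26-week design events unrelated to relapse look modestly more frequent on cariprazine than on placebo

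*SAP*

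**What the plan says.** SAP 11.1 describes treatment-emergent adverse events (TEAEs) in the DBTP as the number and "percentage of patients reporting TEAEs during the DBTP will be tabulated for each treatment group". SAP 11.0 sets the base: "The summarization for the DBTP will use the DB safety population as the denominator". For events leading to discontinuation, SAP 11.1 states: "The incidence of AEs leading to premature discontinuation of IP during the DBTP will be summarized by preferred term and treatment group". This incidence has no time base. For serious events it states: "Summary tables will be provided for patients with TESAEs if these occurred in 5 or more patients". Protocol 7.3.4.1 follows the same pattern. Neither document plans an AE rate per time at risk or a time-to-first-event summary.

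Relapse stops treatment. SAP 4.0: "Patients will continue to receive study treatment until a relapse event occurs or until completion of the 26 weeks of randomized treatment". Protocol 8.9 lists as a mandatory reason for discontinuation: "The patient meets the criteria for relapse during the DB treatment period". SAP 7.1 ends the DBTP at Visit 26 or early termination (ET), so the double-blind AE window closes soon after relapse.

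The planning assumptions in SAP 14.0 are that "the relapse hazard ratio is assumed to be 0.50, and cumulative relapse rate at Week 26 for the placebo group is 46" per cent, with 20% dropout for other reasons by Week 26. On exposure, SAP 9.1 adds: "Patient-years will also be summarized by treatment group for the DBTP for the DB Safety Population". No AE summary draws on those patient-years.

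**The concern.** Both objectives (Protocol 2.1, SAP 5.0) include safety compared with placebo, and Protocol 2.2 words the hypotheses the same way. If cariprazine prevents relapse, its patients stay under double-blind observation longer and have more time in which to report an event. A crude percentage then reflects duration as well as the AE hazard. The better the drug works, the larger the apparent AE excess over placebo for events unrelated to relapse. A reader comparing the arms' columns cannot separate the two parts from the AE tables alone.

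**Working it through.** **Inputs.** From SAP 14.0: placebo relapse 46% at 26 weeks, hazard ratio (HR) 0.50, other dropout 20% at 26 weeks, 115 per arm. AE hazards are not in the documents, so I assume 0.01, 0.02 and 0.04 per week. Event times are taken as exponential and independent unless stated.

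**Weekly hazards.**
- Placebo relapse: −ln(0.54)/26 = 0.0237
- Cariprazine relapse: 0.5 × 0.0237 = 0.01185
- Dropout: g = −ln(0.80)/26 = 0.00858

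**Reproducing the plan's figure.** P(observed relapse) = l/(l+g) × (1 − exp(−26(l+g))), which gives 41.7% on placebo and 23.9% on each cariprazine arm. Then 115 × (0.417 + 2 × 0.239) = 102.9 events, against about 103 stated. Each pair yields 75.4 events and 85.3% power (Schoenfeld), against 85% stated. The inputs therefore match the sponsor's model.

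**Mean double-blind follow-up**, (1 − exp(−(l+g)T))/(l+g):

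| T (weeks) | Placebo | Cariprazine | Ratio |
|---|---|---|---|
| 26 | 17.59 | 20.17 | 1.15 |
| 13 (assumed cut) | 10.62 | 11.42 | 1.08 |
| 8 (assumed cut) | 7.05 | 7.38 | 1.05 |

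At HR 0.7 and T = 26 the ratio is 1.08.

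**Crude AE percentage with equal hazard h in both arms**, h/(h+l+g) × (1 − exp(−(h+l+g)T)), at T = 26:

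| h per week | Placebo | Cariprazine | Ratio | Difference/SE at 115 per arm |
|---|---|---|---|---|
| 0.01 | 15.8% | 18.0% | 1.14 | 0.44 |
| 0.02 | 28.4% | 32.2% | 1.13 | 0.62 |
| 0.04 | 46.9% | 52.4% | 1.12 | 0.84 |

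SE is the square root of [p₀(1−p₀) + p₁(1−p₁)]/115. At HR 0.7 the ratios are 1.07 to 1.08. With follow-up cut at 13 weeks they are about 1.07, and at 8 weeks 1.04 to 1.05 (0.1 to 0.4 SE at 115 per arm over both cuts).

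**Early-onset events.** With a 30% risk confined to weeks 0–4, 0–8 or 0–13 (assumed), the crude ratio is 1.02, 1.04 or 1.07.

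**How the alternatives behave.**
- *First events per time at risk.* Ratio 1.00 under equal constant hazards. For the three early-onset cases it is 0.90, 0.92 and 0.94, in favour of cariprazine, because longer follow-up adds event-free time.
- *Kaplan-Meier (KM) at week 26 (simulated, 400,000 per arm).* Ratio 1.00 when AE and relapse are independent (about 40.5% in both arms at h = 0.02). If they share a gamma frailty of variance 0.5 or 1, with equal true AE risk, KM gives about 1.05 or 1.09, against crude ratios of about 1.17 and 1.2. KM reduces the distortion without removing it.
- *Psychiatric AEs that herald relapse (simulated).* With a background of 0.01 per week, and an AE in the 2 weeks before 10% or 30% of relapses (assumed), the crude ratio is 1.03 or 0.90. The direction is not fixed for these events.
- *Findings seen only at the exit examination (simulated).* With equal true risks of 5% to 23%, KM overstates both arms and gives ratios of 0.88 to 0.92, because placebo patients are examined earlier.

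**The case against.** The strongest reply is that nothing here is an error. The Protocol Summary calls safety analysis descriptive, and SAP 11.1 tabulates without any test or decision rule. SAP 9.1 already gives treatment duration and patient-years by arm, and Appendix IV keeps the exposure summary. Dividing patients with an event by those total patient-years gives ratios of 0.98 to 0.99 at the three assumed hazards, so a reader could make a rough correction. The study was also terminated early (SAP 4.0), so the 26-week figure need not describe the data that exist.

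Most of this stands and limits the point. It does not remove it: a by-hand correction has no interval and cannot use time at risk up to the first event. The abbreviated report still carries double-blind TEAE, serious TEAE and discontinuation summaries.

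A reader might infer more than the documents support:
- *That the tables hide harm.* For AEs unrelated to relapse, the distortion overstates events on cariprazine versus placebo.
- *That the dose comparison is compromised.* The study-design discussion in Protocol section 1 foresees asking whether the lower dose is better tolerated. If both doses have HR 0.50, their expected follow-up is equal. Even HR 0.5 versus 0.7 gives a follow-up ratio of only 1.06 (20.17/19.08).
- *That the ratio of 1.15 holds for the terminated study.* Actual follow-up and arm sizes are not in the documents.
- *That Kaplan-Meier is the unbiased answer.* Censoring at relapse makes it the risk if nobody relapsed or dropped out, which is a hypothetical quantity.

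**Conclusion.** The point holds as a modest reporting gap that should be closed. Under the full planning assumptions, follow-up is 1.15 times as long on cariprazine, and an AE with equal constant hazard shows a crude ratio of 1.12 to 1.14, or 0.4 to 0.8 SE of the difference at 115 per arm. The effect falls to about 1.02 for events in the first 4 weeks, and to 1.04 to 1.07 if follow-up was cut at 8 or 13 weeks. These sizes rest on exponential times, assumed AE hazards and assumed cut-offs. The crude percentage validly describes AEs during assigned treatment, and no error rate is affected. It should not be the only summary from which tolerability against placebo is read. For psychiatric AEs that overlap the relapse criteria in SAP 10.1, no direction can be claimed. Protocol 9.1.1 also keeps anticipated disease worsening out of AE reporting.

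**What to change.** Keep n (%). For any TEAE, serious TEAEs (where the five-patient rule produces the table) and TEAEs leading to discontinuation of investigational product in the DBTP, add by arm:

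1. Patients with a first event per 100 patient-years at risk, with 95% CI, and a note that this rate favours cariprazine for early-onset events.
2. A Kaplan-Meier curve of time to first event, with 95% CI, censored at the end of the DBTP as defined in SAP 7.1 (Visit 26 or ET).

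State beside the curve that it estimates the AE risk if nobody relapsed or dropped out, and that non-informative censoring is doubtful for psychiatric AEs overlapping the relapse criteria.

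For ocular findings seen at the exit examination, do not use Kaplan-Meier. Eye examinations fall at Visits 1, 13 and 26/ET (Protocol 6.5.7), and patients who stop early undergo the Visit 26/ET evaluations (Protocol 8.8). Keep n (%), shown with number examined and time on treatment by arm.

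The cost is low: AE onset, dosing and visit dates are already collected. A few variables must be derived, tables grow slightly, and intervals will be wide if few patients were randomised before termination. The serious-event summary may not be produced at all.

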7.3.4.1 Adverse Events

AEs will be coded by system organ class and preferred term using the *Medical Dictionary for Regulatory Activities* (MedDRA), Version 21.0 or newer.

An AE will be considered a treatment-emergent adverse event (TEAE) if the AE began or worsened (increased in severity or became serious) on or after the first dose of OL IP.

The number and percentage of patients reporting TEAEs during the OL treatment period will be tabulated by system organ class and preferred term, by system organ class, preferred term, and severity, and by system organ class, preferred term, and relationship to IP.

The number and percentage of patients reporting TEAEs during the DB treatment will be tabulated for each treatment group by system organ class and preferred term, by system organ class, preferred term, and severity, and by system organ class, preferred term, and relationship to IP.

The number and percentage of patients reporting TEAEs during the SFU period will be tabulated by system organ class, preferred term, and DB treatment group for the DB safety population and by system organ class and preferred term for the OL safety follow-up population.

For the OL period, DB period, or SFU period, if more than 1 AE was coded to the same preferred term for the same patient, the patient will be counted only once for that preferred term using the most severe and most related occurrence for the summarization by severity and by relationship to IP.

The total number and percentage of TEAEs during the DB treatment period will also be summarized by severity and relationship to IP for each treatment group.

The number and percentage of patients with common ($\geq 2\%$ of patients in any treatment group) TEAEs during the DB treatment period will be summarized by preferred term and treatment group.

An AE that occurs more than 30 days after the last dose of DB IP will not be summarized.

An SAE that occurred between the date of the first dose of IP and 30 days after the date of the last dose of IP, inclusive, will be considered an on-therapy SAE. The number and percentage of patients who had on-therapy SAEs during the OL treatment period and the OL SFU period will be summarized by preferred term. The number and percentage of patients who had on-therapy SAEs during the DB treatment period and the DB SFU period will be summarized by preferred term and DB treatment group.

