17.0 CHANGES TO ANALYSES SPECIFIED IN PROTOCOL

In Section 11.1 (Adverse Events), AE summary timeframe was modified to align with AE reporting period specified in the protocol amendment 4 (dated in December 17th, 2019). The new time frame is defined below.

An AE that occurs more than 30 days after the date of the last dose of DB IP or occurs after the last SFU visit (whichever comes last) will not be summarized except for AEs related to reported pregnancies. AEs associated with pregnancies reported in the protocol-required timeframe up to approximately 12 weeks following the last dose of DB IP will be summarized.

The summary of SAEs was modified in Section 11.1. The definition of on-therapy SAE was updated to TESAE, and summary timeframe will align with general AE summary timeframe as specified above.

18.0

COVID-19 RELATED LISTING

A listing of patients with visits impacted by COVID-19 will be provided.

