APPENDIX IV ANALYSES SPECIFIED FOR ABBREVIATED CSR

On 14 DEC 2020, FDA provided Type C Written Response in which they agreed to release Allergan of the postmarketing requirement (PMR 2947-9) to conduct Study RGH-MD-24, based on new information obtained since initial Vraylar approval in SEP 2015. Study RGH-MD-24 was thus early terminated. The analyses for the abbreviated CSR are the subset of analyses specified in the SAP and listed below. The details are provided in the corresponding SAP sections.

Patient disposition and analysis populations

- Summary of screen failure patients and the associated reasons for failure
- Summary of patient disposition during OLTP and DBTP respectively
- Summary of analysis populations

Demographics and other baseline characteristics

- Summary of demographic and other baseline characteristics, and baseline efficacy variables
- Summary of prior and concomitant medications

Efficacy analyses

- Primary efficacy analysis
- Analyses of change from baseline in the PANSS total score during OLTP and DBTP
- Analyses of change from baseline in BACS composite score

Extent of exposure

- Summary of exposure during OLTP, DBTP and entire study

Safety analyses

- Overall summary of AEs during OLTP, OL Safety Follow-up, DBTP, and DB Safety Follow-up
- Summary of TEAEs during OLTP, OL Safety Follow-up, DBTP, and DB Safety Follow-up

- Summary of treatment-related TEAEs during OLTP and DBTP
- Summary of TEAEs leading to premature discontinuation of IP during OLTP and DBTP
- Summary of ocular events during OLTP, OL Safety Follow-up, DBTP, and DB Safety Follow-up
- Summary of TESAEs during OLTP, OL Safety Follow-up, DBTP, and DB Safety Follow-up
- Summary of TESAEs of ocular events during OLTP and DBTP
- Summary of laboratory PCS during OLTP and DBTP
- Summary of CSSRS during OLTP and DBTP

The following listings will be provided for the abbreviated CSR

- Patients with TEAEs leading to premature discontinuation of IP
- AEs for patients with TEAEs leading to premature discontinuation of IP
- Patients with ocular events
- AEs for patients with ocular events
- Patients who died
- AEs for patients who died
- Patients with SAEs
- Patients with laboratory PCS during OLTP and DBTP
- Patients who meet potential Hy's law criteria during OLTP and DBTP
- Patients with suicidal ideation or behavior
- Patient disposition
- Patients who discontinued OLTP or DBTP
- Patients with protocol deviations

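### SAP 11.1 makes TESAE tables conditional on 5 or more patients, with no unit given, in conflict with its own next sentence, Appendix IV and Protocol 7.3.4.1, and SAP 17.0 does not declare the condition

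*SAP*

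**What the plan says.** SAP 11.1 defines a TESAE as a treatment-emergent adverse event that also meets a seriousness criterion, and then sets the condition: "Summary tables will be provided for patients with TESAEs if these occurred in 5 or more patients". The sentence directly after it has no condition: "The number and percentage of patients with TESAEs will be summarized for OLTP, DBTP, and SFU period". SAP 11.0 supplies the layout for double-blind safety summaries: "by treatment group for the DB period and the DB SFU period in the DB safety population".

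Protocol 7.3.4.1 commits to SAE counts with percentages, and its text for the randomised part of the study reads: "patients who had on-therapy SAEs during the DB treatment period and the DB SFU period will be summarized by preferred term and DB treatment group". It makes the matching commitment by preferred term for the open-label and open-label follow-up periods. Neither has a minimum count.

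SAP 17.0, the section for departures from the protocol, says that the SAE summary in 11.1 was modified. The content it gives is that "The definition of on-therapy SAE was updated to TESAE" and that the time frame now follows the general adverse event time frame. It does not mention a 5-patient threshold.

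SAP Appendix IV, written for the abbreviated report after early termination, lists "Summary of TESAEs during OLTP, OL Safety Follow-up, DBTP, and DB Safety Follow-up" and "Summary of TESAEs of ocular events during OLTP and DBTP". Neither entry has a count condition, but the appendix refers to the SAP sections for details.

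**The concern.** Both study objectives include safety against placebo, and the Protocol Summary says safety is analysed descriptively. No test stands behind the tables, so the by-arm tables are themselves the safety comparison. The protocol's SAE table by preferred term and arm is central to it.

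A rule that produces the table only above a certain count makes its existence depend on the data. With the planned 115 patients per arm, 4 patients with the same serious event in one arm and none in the others is 4/115 = 3.5% against 0% and 0%. If the threshold governs the detailed table, that split would have no preferred-term row with denominators. A reader would have to rebuild it from listings.

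The condition also departs from the protocol without being declared, and a programmer working from 11.1 has two adjacent sentences that cannot both be applied to the same table.

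**Working it through.** The plan states no figure that could be reproduced, so the check is mainly a comparison of text.

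| Source | Breakdown | Minimum count |
|---|---|---|
| Protocol 7.3.4.1 | Preferred term, and double-blind treatment group for the double-blind and its follow-up periods | None |
| SAP 11.1, threshold sentence | Not stated | 5 patients, unit not stated |
| SAP 11.1, next sentence | By period; by arm through SAP 11.0; preferred term not mentioned | None |
| SAP Appendix IV | By period, plus ocular TESAEs; details left to the SAP body | None |
| SAP 17.0 | Declares definition and time frame only | Not mentioned |

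There are two ways to read the adjacent sentences in 11.1.

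1. *They describe the same table.* Then one makes it conditional and the other does not, which is a contradiction.
2. *They describe different tables.* Overall counts per period are always given, and more detailed tables follow only at 5 or more patients. The next sentence, with SAP 11.0, then preserves overall counts by arm. It does not mention preferred term, so the preferred-term-by-arm table that the protocol promises stays conditional.

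On either reading, the SAP does not secure the protocol's table. Appendix IV does not settle the matter, because its reference to the SAP sections leads back to both sentences.

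The rest of 11.1 does not follow the threshold either. SAEs that are extrapyramidal symptoms, a subset of all SAEs, are tabulated by treatment for the double-blind period with no minimum.

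**Illustration only.** Assume the threshold counts double-blind patients pooled over arms, with n patients and a TESAE rate p. Then

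P(fewer than 5) = Σ (k = 0 to 4) C(n,k) p^k (1−p)^(n−k).

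The planned n is 345 (SAP 14.0). The smaller n and all the rates are assumptions.

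| n | p = 1% | p = 2% | p = 3% |
|---|---|---|---|
| 345 (planned) | 0.735 | 0.180 | 0.022 |
| 200 (assumed) | 0.948 | 0.629 | 0.281 |
| 100 (assumed) | 0.997 | 0.949 | 0.818 |

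Now assume instead that the threshold counts patients over the whole study. With the planned 1035 open-label patients and p = 1%, the mean is 1035 × 0.01 = 10.35. The Poisson probability of fewer than 5 is e^(−10.35) × (1 + 10.35 + 53.56 + 184.79 + 478.14) = 0.023.

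At the same 1% rate and planned size, the choice of unit alone moves the answer from 0.735 to 0.023. If the unit is the preferred term, every term seen in 4 or fewer patients drops out, whatever the total.

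**The case against.** The strongest reply is that the plan does not suppress SAE tables. The next sentence of 11.1 gives TESAE counts and percentages by period without a condition, and SAP 11.0 makes them by arm with the double-blind safety population as denominator. Appendix IV, written for the terminated study, keeps the TESAE summary and even lists one for ocular events, where counts might well be small. All patients with SAEs are listed regardless of count. SAP 17.0 does point to 11.1 as the place where the SAE summary changed. The table specifications are in a separate document (SAP 4.0), which may define the unit.

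Most of this stands. A reader might infer that every by-arm SAE count disappears below 5 patients. The documents do not support that: overall counts by arm are promised without a condition, and the listings are complete. A reader might also infer that early termination makes the condition likely to apply. That is unsupported too, because the documents give neither the number randomised nor an SAE rate.

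SAP Appendix V records the removal of a summary with a similar 5-patient condition for discontinuations. This does not show that the SAE threshold is a leftover, since the removed item could have been an additional table.

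The reply leaves three things unresolved. None of the unconditional SAP statements on TESAEs mentions preferred term. The unit of the threshold is undefined in the SAP. The pointer in SAP 17.0 names the definition and the time frame but not the threshold, so disclosure is incomplete.

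**Conclusion.** The point holds as an internal inconsistency with a limited but real consequence. The 5-patient sentence in SAP 11.1 conflicts with the sentence after it, with Appendix IV and with Protocol 7.3.4.1, and it is an undeclared departure from the protocol. What is clearly at risk is the preferred-term-by-arm SAE table. No patient-level SAE information is lost.

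The size cannot be established from the documents. The probabilities above run from about 2% to above 99%, depending on an assumed rate, an assumed sample size and an unstated unit, so they show only that the choice of unit matters. The conclusion rests on the text and does not need them. It is a point to correct in the SAP, and it does not bear on the efficacy analysis.

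**What to change.** Delete the 5-patient sentence from SAP 11.1. In its place, state that TESAE tables by preferred term are always produced, whatever the count: by treatment group for the double-blind and double-blind follow-up periods, and overall for the open-label and open-label follow-up periods. This restores the breakdown in Protocol 7.3.4.1 and agrees with Appendix IV.

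If the sponsor wants a threshold for a supplementary display, name that display, say whether 5 counts patients over the study, per period, per arm or per preferred term, and declare it in SAP 17.0. Check that the separate table specifications follow the same rule.

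The cost is one sentence in the SAP. TESAE summaries for all four periods are already on the Appendix IV list, and no new data are needed.
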